## 8. SUBJECT/PATIENT RECRUITMENT PROCESS

Patient recruitment at a site will only commence once the trial team has ensured that the following approval/essential documents are in place:

- 1. REC approval,
- 2. HRA Approval
- 3. Final sponsorship,
- 4. Local Site Delegation of Duties and Signature Log is completed.

All sites participating in the trial will also be asked to provide a copy of the following:

- 1. Signed Clinical Trial Site Agreement (CTSA) if applicable
- 2. Confirmation of capacity and capability (if applicable).

All subjects who wish to enter the study will be fully screened and consented by the Chief Investigator (CI), or one of the qualified clinicians involved in the study as the local PI or delegated person.

Participants will be recruited from patients who are scheduled to undergo intercostal tube drainage as an in-patient at participating centres. All subjects who wish to enter the study will be fully screened and consented by the Chief Investigator (CI), one of the qualified clinicians involved in the study as the Principal Investigator (PI), or by a delegated person as documented in the study delegation log.

# 9. STUDY PROCEDURES

### 9.1 INFORMED CONSENT

Informed consent will be obtained by the Chief Investigator (CI), Principle Investigator (PI) and/or a nominated deputy as recorded on Sponsor's Delegation of Responsibilities Log. All individuals taking informed consent will have received consent training.

Consent to enter this study will be obtained after a full account has been provided of its nature, purpose, risks, burdens and potential benefits, and the patient has had the opportunity to deliberate. The patient will be allowed to specify the time they wish to spend deliberating, usually up to 24 hours.

Periods shorter than 24 hours will be permitted if the patient feels that further deliberation will not lead to a change in their decision, and provided the person seeking consent is satisfied that the patient has fully retained, understood and deliberated on the information given. This provision has been made with the support of our patient advisory group. Patients in severe acute pain will not be approached and all patients will be allowed at least 1 hour to consider whether they would be happy to participate.

Likewise, periods longer than 24 hours will be permitted should the patient request this. The Investigator or designee will explain that the patients are under no obligation to enter the trial and that they can withdraw at any time during the trial, without having to give a reason.

A copy of the signed Informed Consent Form (ICF) along with a copy of the most recent approved Patient Information Sheet (PIS) will be given to the study participant. The original signed consent form will be retained at the study site (one filed in the medical notes and one filed in the Investigator Site File (ISF)) A copy of the consent form will also be given to the patient.

If new safety information results in significant changes to the risk-benefit assessment, the consent form will be reviewed and updated if necessary. All subjects, including those already being treated, will be informed of the new information, given a copy of the revised consent form and asked to re-consent if they choose to continue in the study.

### 9.2 RANDOMISATION PROCEDURE

Once a patient has been identified for the trial and has signed the informed consent form, baseline details as listed in section 10.2 will be entered into a dedicated webbased programme accessible at all sites, and patients will be allocated 1:1 to either usual care (a standard 12F ICT) or to the interventional drain, minimised by sites and disease areas (MPE/infection/pneumothorax/other).

### **10.STUDY ASSESSMENTS**

### 10.1 SCREENING ASSESSMENTS

All patients requiring intercostal drainage for clinical reasons will be offered entry into the study, unless, in the view of the treating physician, large bore drain is required. No other screening assessments will be required, other than the ability to sign the informed consent form.

### **10.2 BASELINE ASSESSMENTS**

No changes to usual clinical care occur as part of the trial, and no additional baseline assessments will be made. The following baseline data will, however, be collected:

- Primary diagnosis requiring intercostal drain
- Laterality of pleural disease requiring intervention
- Co-morbidities
- Previous thoracic intervention(s).

- Age
- Sex
- Body habitus

### **10.3 TREATMENT PROCEDURE**

Patients who have provided signed informed consent will then proceed to the study protocol. Patients will be randomised to undergo either standard ICT insertion (usual clinical care) or insertion of the interventional drain.

Standard clinical policies and procedures at each participating centre will be followed for chest drain insertion, and no additional procedures or tests will be required for those randomised to the interventional drain.

The procedure will be performed under local anaesthesia with standard monitoring according to local protocol.

Data collected at the time of insertion will include:

- Laterality
- Site of drain insertion (using visual scale)
- Volume and strength of local anaesthetic used
- Analgesia administered
- Use of ultrasound at time of drain insertion and findings thereof including depth from skin to pleura.
- Number of centimeters to which drain was inserted
- Size of drain

### **10.4 SUBSEQUENT ASSESSMENTS**

All subsequent care will be as per best clinical care for all patients in both arms of the study. The only additional assessments over and above usual care will be the collection of pain scores. Pain will be rated by the patients on a visual analogue scale (VAS).

Patients will be asked to draw a line perpendicular to a 10cm long horizontal line, where the left hand end relates to no pain at all, and the right to the worst pain imaginable. This score will be recorded twice daily by the patient in a VAS booklet, until drain removal or day 5 post insertion, whichever is sooner.

Data collected whilst the original drain is in situ will include:

- Analgesia used
- Additional stitches needed

- Any complications
- VAS scores (To be filled in by the patient twice daily)

Data collected at the time of drain removal will include

- Date of drain displacement or intentional removal
- Clinical decision re drain removal (disease specific criteria)
- Number of centimeters at the skin at the time of removal
- Balloon integrity at the time of removal? (Intervention arm)

Data collected at the time of discharge will include:

- Number of further pleural procedures needed
- Any further complications since drain removal

Data will be collected at 30 days (+/- 7 days) post drain removal (either in clinic or via safety follow-up telephone call). If the patient is being contacted by telephone, their medical records will be reviewed prior to contacting to ensure that contact is appropriate. The patient will then be asked some screening questions when contacted to ensure that capacity has been retained and that it is appropriate to continue with the follow up call. The data collected from the patient and their medical notes will include:

- Complications
- Final diagnosis
- Further pleural interventions
- Total number of days any chest drain was in situ, including the original drain.

Final diagnosis will be confirmed on meeting one of the criteria below:

Malignant pleural effusion diagnosis is made by one of the following:

- Histological or cytological diagnosis of pleural malignancy OR
- pleural effusion in the context of histologically proven cancer elsewhere

Pleural infection diagnosis is made by one of the following:

- Pleural fluid pH of ≤7.2 in the context of infection OR
- Pleural fluid glucose ≤3.4 in the context of infection OR
- Strong clinical suspicion of pleural infection provided by clinical or radiological information OR
- Frank pus in the pleural space or positive microbiology from pleural fluid samples

Pneumothorax is defined as air in the pleural space.

Other causes include parapneumonic effusions, hydropneumothorax, transudative effusions, reactive effusions, effusion of unknown aetiology and these data will be collected on the appropriate CRFs.

The final point of data collection will be 30 days (+/- 7 days) after the original chest drain was removed. If the patient is still an inpatient at this point both the discharge CRF and follow up CRF should be completed at this point. If it is not possible to

contact the patient the 30 day CRF should be completed using the medical notes and any other available information.

All data will be anonymised and stored according to ORTU standard operating procedures.

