### 11.4 DEFINITION OF THE END OF TRIAL

The end of the trial is defined as the Last Patient Last Visit (LPLV), that is when the final patient has completed their 30 day (+/- 7 days) post drain removal safety telephone call or completed a 30 day review (+/- 7 days), if routinely being seen in clinic.

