# **Foreseeable Events**

A large proportion of patients in this study are likely to have life limiting diseases. Patients with malignant pleural effusions who have been hospitalized have a 30 day mortality of 15% (6) and those with pleural infection have a 20% 3 month mortality. In this study, therefore, using the conventional timelines for adverse event reporting is not appropriate.

Disease related expected SAEs include: re-admission, death, and disease progression as judged by the local PI (or delegated person if the PI is unavailable). These will be recorded on the CRFs as expected adverse events but not subject to the timelines for SAE reporting.

Drain related expected AEs include: pain, infection, bleeding, organ puncture, hypoxia, persistent air leak, surgical emphysema, hypotension and prolonged length

of stay due to drain removal/displacement. All drain related adverse events as judged by the local PI (or delegated person if the PI is unavailable) will be captured on the CRFs up to 30 days after initial drain removal. At the 30 day telephone / clinical follow up point, CRFs will be used to record any further defined adverse events. Only those which are directly attributable to drain insertion / use / removal will be recorded at this point.

Unexpected adverse events are those not on the list above that in the investigators view is directly attributable to the chest drain. If these are serious (i.e. Serious and Unexpected Adverse Event), these events will be subject to expedited reporting to the sponsor as per SUSAR guidelines.

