### 12.4 THE TYPE AND DURATION OF THE FOLLOW-UP OF SUBJECTS AFTER SAES

All SAEs will be treated as per clinical need, and follow-up will be arranged with the relevant PI in the out-patient department to monitor progress from adverse events if felt necessary on discharge. Adverse events will be recorded on the CRFs up to and including the 30 day month safety follow-up telephone call/clinic review.

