# 14.2.2 Secondary endpoints

- 1. To assess the difference in patient reported pain scores, using a visual analogue scale.
- assessed by simple measurement of the distance of the line drawn by the patient from the left hand end of the VAS.2. To assess the frequency complications such as balloon rupture, drain blockage or other drain related complications
  - Assess balloon rupture in the interventional arm only, by inflation of the balloon with fluid after removal (accidental or intentional) from the pleural space.
  - Assessed by review of medical notes or patient review whilst the original chest drain is in situ
- 3. To assess the difference in the length of hospital stay
  - Record the number of days, after insertion of the initial study drain, that the patient was discharged (Including day of drain insertion and date of discharge)
- 4. To assess the total number of pleural procedures (including surgical procedures) in the 30 days after the initial study drain was removed
  - Record the number of pleural procedures undertaken in the 30 days after the initial study drain was removed
- 5. To assess the number of days which the patient has any chest drain in situ in the 30 days after the initial drain removal
  - Record the number of days the patient had a chest drain in situ in the 30 days after the initial study drain was removed after the initial study drain was removed
- 6. To record the total number of radiological investigations performed from the time of drain insertion until the 30 day follow up has been completed
  - Assessed by review of medical notes radiology systems.
- 7. To record the consequences of drain displacement such as failed treatment, delayed discharge the need for subsequent pleural procedures or the need for further medical or surgical care
  - Assessed by review of medical notes and/or patient review.

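### Final data collection may close from day 23, although two secondary endpoints and drain-related adverse event capture are defined to day 30

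*Protocol*

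**What the plan says.** Protocol section 10.4 sets the follow-up contact: "Data will be collected at 30 days (+/- 7 days) post drain removal (either in clinic or via safety follow-up telephone call". It then makes that contact the end of collection: "The final point of data collection will be 30 days (+/- 7 days) after the original chest drain was removed". Section 11.4 repeats the tolerance in defining the end of the trial, which comes "when the final patient has completed their 30 day (+/- 7 days) post drain removal safety telephone call" or the equivalent clinic review. Section 13.3 has the investigator complete the dataset from the notes and electronic record at the time of that call or review. No later look-up is stated. Under section 10.4, a patient who is still in hospital at that point has both the discharge form and the follow-up form completed then.

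The outcomes that depend on this contact have these windows:

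- Endpoint 4 (section 14.2.2): "Record the number of pleural procedures undertaken in the 30 days after the initial study drain was removed".
- Endpoint 5 (section 14.2.2): "Record the number of days the patient had a chest drain in situ in the 30 days after the initial study drain was removed". The item that section 10.4 lists for the follow-up contact is different: "Total number of days any chest drain was in situ, including the original drain".
- Endpoint 6, radiological investigations (section 14.2.2): from drain insertion until the follow-up is completed.
- Drain-related adverse events: section 12.1 (Foreseeable Events) says they "will be captured on the CRFs up to 30 days after initial drain removal", while section 12.4 says "Adverse events will be recorded on the CRFs up to and including the 30 day month safety follow-up telephone call/clinic review".

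**The concern.** A fixed 30-day count needs 30 days of observation. The protocol fixes the count at 30 days but lets observation stop a week earlier, and it ties the records review to the same early date. A site that telephones on day 23 has followed the protocol and has no stated reason to look again at days 24 to 30.

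At stake are late repeat procedures, late drain-days and late drain-related harm. Patients who are still in hospital with a drain in place show this most plainly: if such a patient's forms are completed on day 23, up to 7 drain-days are missing from endpoint 5. Capture of harm matters too, because the pilot of the interventional drain had only 20 patients (section 4.3).

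This cannot be left to the analysis plan. An analysis can cut a long observation period at day 30, but it cannot fill in days that nobody recorded.

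**Working it through.** **Inputs from the protocol.** Contact at day 30 with a tolerance of 7 days either way (sections 10.4 and 11.4); count window of 30 days from removal of the initial drain (section 14.2.2, endpoints 4 and 5; section 12.1 for drain-related events). The protocol gives no event rates or timing for these outcomes, so the timing shapes below are assumptions.

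**Window.** Earliest contact: 30 − 7 = day 23. Latest: 30 + 7 = day 37. A day-23 contact leaves days 24 to 30 unobserved: 7/30 = 23% of the window.

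**Share of events lost at a day-23 closure.** Let F(t) be the cumulative expected count by day t. Loss = 1 − F(23)/F(30).

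- Constant rate, F(t) proportional to t: 1 − 23/30 = 23%.
- Rate halving every h days, F(t) proportional to 1 − 2^(−t/h):
  - h = 14: 1 − 0.6798/0.7736 = 12%
  - h = 7: 1 − 0.8975/0.9487 = 5%
  - h = 3: 1 − 0.9951/0.9990 = 0.4%

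**Mean loss if contacts are spread evenly over the 15 days from 23 to 37, with late counts capped at day 30.** Mean loss = (1/15) × Σ max(0, 1 − F(t)/F(30)), for t = 23 to 37.

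- Constant rate: the missed days are 7 + 6 + 5 + 4 + 3 + 2 + 1 = 28, so 28/(15 × 30) = 6.2%.
- h = 14, 7, 3: 3.1%, 1.3%, 0.1%.

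| Assumed event timing | Loss at day 23 | Mean loss, even spread |
|---|---|---|
| Constant rate | 23% | 6.2% |
| Half-life 14 days | 12% | 3.1% |
| Half-life 7 days | 5% | 1.3% |
| Half-life 3 days | 0.4% | 0.1% |

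If collection never closes before day 30 and counts stop at day 30, the loss is zero in every row.

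**Windows side by side.**

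| Outcome | Stated end of window | Consistent with a contact at day 23 to 37? |
|---|---|---|
| Endpoint 4 | Day 30 | Not observed to day 30 if contact is earlier |
| Endpoint 5 | Day 30 | Same. The section 10.4 item also has no cap and includes the original drain, so it starts before the endpoint's clock and cannot give endpoint 5 alone |
| Drain-related events | Day 30 (12.1); date of contact (12.4) | The two sections disagree whenever contact is not on day 30 |
| Endpoint 6 | Date of contact | Length varies from patient to patient |

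**The case against.** A symmetric window is a common pragmatic choice, only secondary and safety counts are touched, and 23% is a share of days in the extreme case rather than an expected share of events. All of that stands. It limits the size of the problem but does not close the gap for contacts before day 30.

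Three stronger readings are tempting, and the protocol does not support them.

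- **Late contacts inflate endpoints 4 and 5.** One might infer that a day-37 call yields up to 37/30 = 123% of the proper count, or that patients are counted over periods differing by 37/23 = 1.6. But section 14.2.2 limits both counts to the 30 days after removal, so a late contact that follows the definition gives a 30-day count. The short item labels in section 10.4 are not the case report form. Some timing is also required: section 6.2.2 has the timing of further drain insertion and drainage time recorded when a displaced drain is re-sited, section 10.4 asks for the date of displacement or removal, and section 10.5 asks when re-siting occurred. These do not cover every procedure after discharge, but it would be wrong to say that no dates are collected.
- **Harm after an early call is never seen.** Section 12.3 keeps reporting of related, unexpected serious events open until 30 days after initial drain removal. The exposed part is the rest of drain-related event capture, where sections 12.1 and 12.4 conflict.
- **The comparison between arms is biased.** The same window applies to both arms and to clinic and telephone contact. Bias would need contact timing to differ by arm, and nothing in the protocol shows that it does. As an outer limit, at a constant rate with late counts capped, one arm contacted entirely on day 23 and the other on day 30 or later would give a spurious ratio of 30/23 = 1.30.

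**Conclusion.** The point holds for truncation. Within protocol, follow-up and its records review can close up to 7 days before the end of the window that defines endpoints 4 and 5 and drain-related event capture. The loss for a patient closed on day 23 ranges from 23% of the 30-day count (constant rate) down to 0.4% (half-life 3 days). The mean over evenly spread contacts ranges from about 6% down to 0.1%. These figures rest on assumed event timing and an assumed spread of contact dates, neither of which the protocol gives.

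Three smaller inconsistencies go with it: the drain-days item in section 10.4 cannot alone produce endpoint 5, sections 12.1 and 12.4 end adverse event recording at different times, and the window for endpoint 6 moves with the contact date.

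Over-run of endpoints 4 and 5 is not shown, and neither is bias between arms. The primary endpoint, which concerns displacement before a clinical decision to remove or reposition the drain, does not depend on this contact, and the sample size is unaffected. This is an inexpensive improvement to secondary and safety data.

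**What to change.** - In sections 10.4, 11.4 and 13.3, do not let the final contact, or at least the records check that completes the 30-day form, close before day 30; a window of day 30 to day 37 would do.
- Record the dates of pleural procedures, of every drain insertion and removal, and of drain-related adverse events, so that counts stop at day 30 for everyone. Derive endpoint 5 from those dates rather than from the total in section 10.4.
- Reconcile sections 12.1 and 12.4, and endpoint 6 in section 14.2.2, to the same 30-day limit.

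The cost is a few wording changes, date fields where the form does not already have them, and less scheduling flexibility for sites. Patients whose routine clinic review falls on days 23 to 29 would need a later notes check or a call, because that review could no longer close their follow-up by itself.

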### 10.5 SUMMARY CHART OF STUDY ASSESSMENTS

	Insertion	Day 0-5	Removal	Discharge
Pain score	/	/	/	
Drain re-sited?		/	/	
- If so, when and why?				
Complications?	/	/	/	/
Further pleural procedures			/	/
Balloon intact?				/
Total days drain in situ				/
Total hospital stay				/

### 11.METHODS

## 11.1 LABORATORY PROCEDURES

No samples will be taken, and no laboratory procedures will be undertaken other than those required as part of usual clinical care.

# 11.2 RADIOLOGY OR ANY OTHER PROCEDURE(S)

No additional radiology procedures are undertaken as part of this trial but data will be collected from radiological investigations conducted as part of clinical care.

### 11.3 TECHNIQUES AND INTERVENTIONS

# 11.3.1 Description of interventional drain

The Rocket ballooned drain is similar in design to standard small bore intercostal drains, except for the addition of an inflatable balloon between 8cm and 10cm from the drain tip (figure 1) which is inflated using sterile water *via* a separate inflation channel running within the wall of the drain (figure 2). Although the balloon is capable of accommodating a greater volume of fluid, it is recommended that 5mls of

fluid be used for inflation. This will minimise the risk of balloon rupture or tissue injury whilst providing ample volume to prevent the balloon from regressing through the thoracostomy site. Detailed drawings can be found in appendix 2.

Figure 1: Picture showing position of balloon

Figure 2: Picture showing syringe attached to balloon inflation channel

### 11.4 DEFINITION OF THE END OF TRIAL

The end of the trial is defined as the Last Patient Last Visit (LPLV), that is when the final patient has completed their 30 day (+/- 7 days) post drain removal safety telephone call or completed a 30 day review (+/- 7 days), if routinely being seen in clinic.

### 12. SAFETY REPORTING

# 12.1 **DEFINITIONS**

Adverse Event (AE)	Any untoward medical occurrence in a participant to whom a medicinal product has been administered, including occurrences which are not necessarily caused by or related to that product.					
Adverse Reaction (AR)	An untoward and unintended response in a participant to an investigational medicinal product which is related to any dose administered to that participant.  The phrase "response to an investigational medicinal product" means that a causal relationship between a trial medication and an AE is at least a reasonable possibility, i.e. the relationship cannot be ruled out.  All cases judged by either the reporting medically qualified professional or the Sponsor as having a reasonable suspected causal relationship to the trial medication qualify as adverse reactions.					
Serious Adverse Event	A serious adverse event is any untoward medical					
(SAE)	occurrence that:					
	• results in death					
	is life-threatening     requires inpatient bespitalisation or prolongation of					
	
 
requires inpatient hospitalisation or prolongation of existing hospitalisation
 
					
	
 
results in persistent or significant disability/incapacity
 
					
	• consists of a congenital anomaly or birth defect.					
	Other 'important medical events' may also be considered					
	serious if they jeopardise the participant or require an					
	intervention to prevent one of the above consequences.					
	NOTE: The term "life-threatening" in the definition of					
	"serious" refers to an event in which the participant was at risk of death at the time of the event; it does not refer to					
	an event which hypothetically might have caused death if it					
	were more severe.					
Serious Adverse	An adverse event that is both serious and, in the opinion of					
Reaction (SAR)	the reporting Investigator, believed with reasonable					
	probability to be due to one of the trial treatments, based					
	on the information provided.					

